##### *Glucose Alert Value (Level 1):*

- **Documented symptomatic hypoglycemia** is defined as any time a participant feels that he or she is experiencing symptoms and/or signs associated with hypoglycemia and has a BG level of  $<70$  mg/dL ( $<3.9$  mmol/L).
- **Documented asymptomatic hypoglycemia** is defined as any event not accompanied by typical symptoms of hypoglycemia, but with a measured BG  $<70$  mg/dL ( $<3.9$  mmol/L).
- **Documented unspecified hypoglycemia** is defined as any event with no information about symptoms of hypoglycemia available, but with a measured BG  $<70$  mg/dL ( $<3.9$  mmol/L).

##### *Clinically Significant Hypoglycemia (Level 2):*

- **Documented symptomatic hypoglycemia** is defined as any time a participant feels that he or she is experiencing symptoms and/or signs associated with hypoglycemia and has a BG level of  $<54$  mg/dL ( $<3.0$  mmol/L).
- **Documented asymptomatic hypoglycemia** is defined as any event not accompanied by typical symptoms of hypoglycemia but with a measured BG  $<54$  mg/dL ( $<3.0$  mmol/L).

- **Documented unspecified hypoglycemia** is defined as any event with no information about symptoms of hypoglycemia available but with a measured BG <54 mg/dL (<3.0 mmol/L).

***Severe hypoglycemia (Level 3):***

- **Severe hypoglycemia** is defined as an episode with severe cognitive impairment, requiring the assistance of another person to actively administer carbohydrate, glucagon, or other resuscitative actions. These episodes may be associated with sufficient neuroglycopenia to induce seizure or coma. Blood glucose measurements may not be available during such an event, but neurological recovery attributable to the restoration of BG to normal is considered sufficient evidence that the event was induced by a low BG concentration.

To avoid duplicate reporting, all consecutive BG values <70 mg/dL (<3.9 mmol/L) occurring within a 1-hour period may be considered to be a single hypoglycemic event (Weinberg et al. 2010; Danne et al. 2013).

### 8.3.2.2. Pancreatitis

#### *Diagnosis of Acute Pancreatitis*

Acute pancreatitis is an AE of interest in all studies with tirzepatide, including this study. The diagnosis of acute pancreatitis requires 2 of the following 3 features (Banks and Freeman 2006; Koizumi et al. 2006):

- abdominal pain, characteristic of acute pancreatitis (that is, epigastric pain radiating to the back, often associated with nausea and vomiting)
- serum amylase (total, pancreatic, or both) and/or lipase  $\geq 3X$  ULN
- characteristic findings of acute pancreatitis on CT scan or magnetic resonance imaging (MRI)

If acute pancreatitis is suspected, the investigator should:

- obtain appropriate laboratory tests, including pancreatic amylase (p-amylase) and lipase
- perform imaging studies, such as abdominal CT scan with or without contrast, abdominal MRI, or gallbladder ultrasound

**Note:** Abdominal ultrasound may be used as an alternative method only if CT and MRI cannot be performed.

- evaluate for possible causes of acute pancreatitis, including alcohol use, gallstone/gall bladder disease, hypertriglyceridemia, and concomitant medications

#### *Discontinuation for Acute Pancreatitis*

If acute pancreatitis is diagnosed, the participant must discontinue use of the study intervention.

#### *Case Adjudication and Data Entry*

An independent clinical endpoint committee (CEC) will adjudicate all suspected cases of acute pancreatitis. In addition, AEs of severe or serious abdominal pain of unknown etiology will also

be submitted to the adjudication committee to assess for possible pancreatitis or other pancreatic disease.

#### ***Asymptomatic Elevation of P-Amylase and/or Lipase***

Serial measures of pancreatic enzymes have limited clinical value for predicting episodes of acute pancreatitis in asymptomatic patients (Nauck et al. 2017; Steinberg et al. 2017a, 2017b). Therefore, further diagnostic follow-up of cases of asymptomatic elevation of pancreatic enzymes (lipase and/or p-amylase  $\geq 3$ X ULN) is not mandated but may be performed based on the investigator's clinical judgment and assessment of the participant's overall clinical condition.

#### **8.3.2.3. Thyroid Malignancies and C-Cell Hyperplasia**

Individuals with personal or family history of MTC and/or MEN-2 will be excluded from the study. Participants who are diagnosed with MTC and/or MEN-2 during the study will have study drug stopped and should continue follow-up with an endocrinologist.

The assessment of thyroid safety during the trial will include reporting of any case of thyroid malignancy (including MTC, papillary carcinoma, and others) and measurements of calcitonin. These data will be captured in specific eCRFs. The purpose of calcitonin measurements is to assess the potential of tirzepatide to affect thyroid C-cell function, which may indicate development of C-cell hyperplasia and neoplasms.

#### **8.3.2.4. Calcitonin Measurements**

If an increased calcitonin value (see definitions below) is observed in a participant who has been administered a medication that is known to increase serum calcitonin, then this medication should be stopped, and calcitonin levels should be measured after an appropriate washout period.

For participants who require additional endocrine assessment because of increased calcitonin concentration as defined in this section, data from the follow-up assessment will be collected in the specific section of the eCRF.

#### ***Calcitonin Measurements in Participants with eGFR $\geq 60$ mL/min/1.73 m^2***

A significant increase in calcitonin for participants with eGFR  $\geq 60$  mL/min/1.73 m^2 is defined below. If a participant's laboratory results meet these criteria, these clinically significant laboratory results should be recorded as an AE.

- *Serum calcitonin value  $\geq 20$  ng/L and  $< 35$  ng/L AND  $\geq 50\%$  increase from the screening value.* These participants will be asked to repeat the measurement within 1 month. If this repeat value is increasing ( $\geq 10\%$  increase), the study drug should be stopped, and the participant encouraged to undergo additional endocrine assessment and longer-term follow-up by an endocrinologist to exclude any serious adverse effect on the thyroid.
- *Serum calcitonin value  $\geq 35$  ng/L AND  $\geq 50\%$  over the screening value.* In these participants, study drug should be stopped, and the participant recommended to immediately undergo additional endocrine assessments and longer-term follow-up by an endocrinologist.

***Calcitonin Measurement in Participants with eGFR <60 mL/min/1.73 m^2***

A significant increase in calcitonin for participants with eGFR <60 mL/min/1.73 m^2 is defined as a *serum calcitonin value ≥35 ng/L AND ≥50% over the screening value*. If a participant's labs meet these criteria, these clinically significant labs should be recorded as an AE.

In these participants, study drug should be discontinued (after first confirming the value) and the participant recommended to immediately undergo additional endocrine assessments and longer-term follow-up by an endocrinologist to exclude any serious adverse effect on the thyroid.

**8.3.2.5. Major Adverse Cardiovascular Events**

Deaths and nonfatal cardiovascular AEs will be adjudicated by a committee of physicians external to Lilly with cardiology expertise. This committee will be blinded to treatment assignment. The nonfatal cardiovascular AEs to be adjudicated include

- myocardial infarction
- hospitalization for unstable angina
- hospitalization for heart failure
- coronary interventions (such as coronary artery bypass graft or percutaneous coronary intervention), and
- cerebrovascular events, including cerebrovascular accident (stroke) and transient ischemic attack.

**8.3.2.6. Supraventricular Arrhythmias and Cardiac Conduction Disorders**

Treatment-emergent cardiac conduction disorders will be further evaluated. Participants who develop any event from these groups of disorders should undergo an ECG, which should be submitted to the central reading center. Additional diagnostic tests to determine exact diagnosis should be performed, as needed. The specific diagnosis will be recorded as an AE. Events that meet criteria for serious conditions as described in Section 10.4 must be reported as SAEs.

**8.3.2.7. Hypersensitivity Reactions**

Many drugs, but particularly biologic agents, carry the risk of systemic hypersensitivity reactions. If such a reaction occurs, additional data describing each symptom should be provided to the sponsor in the eCRF.

Sites should have appropriately trained medical staff and appropriate medical equipment available when study participants are receiving study drug. It is recommended that participants who experience a systemic hypersensitivity reaction be treated per national and international guidelines.

In the case of generalized urticaria or anaphylaxis, additional blood and urine samples should be collected as described in Section 10.3, Appendix 3: "Laboratory Assessments for Hypersensitivity Events." Laboratory results are provided to the sponsor via the central laboratory.

### **8.3.2.8. Injection-Site Reactions**

Symptoms of a local injection site reaction may include erythema, induration, pain, pruritus, and edema. If an injection site event is reported, the AE will be recorded, and additional data will be provided to the sponsor in the Injection Site Reaction eCRF.

At the time of AE occurrence, samples will be collected for measurement of tirzepatide antidrug antibodies (ADAs) and tirzepatide concentration.

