## 8.9. Immunogenicity Assessments

Where local regulations and ERBs allow, blood samples for immunogenicity testing will be collected to determine antibody production against tirzepatide as specified in the SoA (Section 1.3).

For immunogenicity testing, venous blood samples will be collected from each participant according to the SoA (Section 1.3) to determine antibody production against tirzepatide. To interpret the results of immunogenicity, a venous blood sample will be collected at the same time points to determine the plasma concentrations of tirzepatide. All samples for immunogenicity should be taken predose when applicable and possible.

In the event of systemic drug hypersensitivity reactions (immediate or nonimmediate), additional unscheduled samples should be collected as detailed in Section 8.3.2.7 (Hypersensitivity Reactions). Instructions for the collection and handling of blood samples will be provided by the sponsor. The actual date and time (24-hour clock time) of each sampling will be recorded. Samples collected at Visit 801 will assess immunogenicity at washout of tirzepatide (5 half-lives post end of treatment).

Immunogenicity will be assessed by a validated assay designed to detect ADAs in the presence of tirzepatide at a laboratory approved by the sponsor. Antibodies may be further characterized for their ability to neutralize the activity of tirzepatide on GIPR and GLP-1R. Positive tirzepatide ADA samples will be tested for cross-reactivity with native GIP and GLP-1, and, if positive, may then be tested for neutralizing antibodies against native GIP and/or GLP-1. In vivo laboratory indicators for effect on weight loss and PK will be utilized to detect potential neutralizing effect of ADAs against tirzepatide.

Treatment-emergent ADAs are defined in Section 9.4.5.

Samples will be retained for a maximum of 15 years after the last participant visit, or for a shorter period if local regulations and ERBs allow, at a facility selected by the sponsor. The duration allows the sponsor to respond to future regulatory requests related to tirzepatide. Any samples remaining after 15 years will be destroyed.

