### Clinical Lab Tests for Hypersensitivity Events

Hypersensitivity Tests	Notes
	Selected test may be obtained in the event of anaphylaxis or systemic allergic/hypersensitivity reactions.
Tirzepatide ADAs (immunogenicity)	Assayed by Lilly-designated laboratory. Results will not be provided to the investigative sites.
Tirzepatide concentrations (PK)	Assayed by Lilly-designated laboratory. Results will not be provided to the investigative sites.
Tryptase	Assayed by Lilly-designated laboratory. Results will not be provided to the investigative sites.  Note: If a tryptase sample is obtained more than 2 hours after the event (that is, within 2 to 12 hours), or is not obtained because more than 12 hours have lapsed since the event, obtain urine sample for N-methylhistamine testing. Note that for tryptase serum samples obtained within 2 to 12 hours of the event, urine N-methylhistamine testing is performed in addition to tryptase testing. Collect the first void urine sample following the event. Obtain a follow-up urine sample for N-methylhistamine testing at the next regularly scheduled visit or after 4 weeks, whichever is later.
N-methylhistamine	Assayed by Lilly-designated laboratory. Results will not be provided to the investigative sites.
Drug-specific IgE	Will be performed if a validated assay is available.  Assayed by Lilly-designated laboratory. Results will not be provided to the investigative sites.
Basophil activation test	Will be performed if a validated assay is available.  Assayed by Lilly-designated laboratory. Results will not be provided to the investigative sites.  Note: The basophil activation test is an in vitro cell-based assay that only requires a serum sample. It is a surrogate assay for drug-specific IgE, but is not specific for IgE.
Complement (C3, C3a, and C5a)	Assayed by Lilly-designated laboratory. Results will not be provided to the investigative sites.
Cytokine panel (IL-6, IL-1 $\beta$ , IL-10)	Assayed by Lilly-designated laboratory. Results will not be provided to the investigative sites.

Abbreviations: ADA = antidrug antibody; IgE = immunoglobulin E; IL = interleukin; PK = pharmacokinetic.

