4.6.5.5.2. Definitions of Immunogenicity Assessment Periods

Immunogenicity Baseline Observations: Baseline period for immunogenicity assessment for each participant includes all observations prior to first dose of study treatment. In instances where multiple baseline observations are collected, to determine participant ADA status the last nonmissing immunogenicity assessment prior to first administration of study drug is used to determine treatment-emergent status (see below).

Immunogenicity Postbaseline Period Observations: Postbaseline period observations for each participant includes all observations after the first administration of study drug. There are 2 different periods listed below:

- The planned treatment period is defined as from the first dose of treatment to end of the treatment period.
- The entire postbaseline period is defined as from the first dose of treatment to the end of safety follow-up visit or date of study withdrawal

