4.6.5.5.3. Definitions of Participant ADA Status

Participant evaluable for TE ADA: a participant has a nonmissing baseline ADA result, and at least 1 nonmissing postbaseline ADA result.

Treatment-emergent ADA-unevaluable participant: any participant who does not meet the evaluable criteria.

Baseline ADA Present (preexisting antibody): ADA detected in a sample collected up to the first dose date and time.

Baseline ADA Not Present: ADA is not detected, and the corresponding PK concentration is missing or below the drug tolerance limit in a sample collected up to the first dose date and time.

Treatment-emergent ADA positive (TE ADA+) participant: A participant who is evaluable for TE ADA is TE ADA+ if either of the following holds:

- The participant has baseline status of ADA Not Present and at least 1 postbaseline status of ADA Present with titer $\geq 2 \times$ MRD of the ADA assay.
- The participant has baseline and postbaseline status of ADA Present, with the postbaseline titer being 2 dilutions (4-fold) greater than the baseline titer. That is, the participant has baseline (B) status of ADA Present, with titer 1:B, and at least 1 postbaseline (P) status of ADA Present, with titer 1:P, with P/B ≥ 4 .

As shown in [Figure GPHN.4.1](#), a titer is expected when ADA assay result is detected. On occasion, the corresponding assay cannot be performed, in which case a titer value will be imputed for the purpose of TE ADA determination. A baseline sample with detected ADA and no titer is imputed to be the MRD (1:10), and a postbaseline sample with ADA detected and no titer is imputed to be 1 dilution above the MRD (1:20).

Treatment-emergent ADA inconclusive participant: A TE ADA-evaluable participant is TE ADA inconclusive if $\geq 20\%$ of the participant's postbaseline samples are ADA inconclusive and all remaining postbaseline samples are ADA not present.

Treatment-emergent ADA negative (TE ADA-) participant: A TE ADA evaluable participant is TE ADA- when the participant is not TE ADA+ and not TE ADA inconclusive.

For each NAb assay, the following are defined:

NAb-positive (NAb+) participant: A participant who is TE ADA+ and has a NAb+ sample in the postbaseline period.

NAb-inconclusive participant: A participant who is TE ADA+, is not NAb+, and all samples that have TE ADA+ titer have a NAb-inconclusive sample result.

NAb-negative (NAb-) participant: A participant who is neither NAb+ nor NAb inconclusive.

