4.6.5.5.4. Analyses to be Performed

Two analysis sets will be considered:

- mITT analysis set: refer to Section 3. Note that for mITT population, only time during tirzepatide exposure will be summarized.
- For participants who randomized to tirzepatide MTD arm.

The analysis period was defined in Section [4.6.5.5.2](#). The count and proportion of participants who are TE ADA+ will be tabulated, where proportion are relative to the number of participants who are TE ADA evaluable, as defined above. The tabulation will include the number and proportion of participants with ADA Present at baseline, and the number and proportion of TE ADA+ participant exhibiting each type of cross-reactive antibodies and NAb. *In silico* classification for cross-reactive NAb will be summarized.

A summary will be provided of the count and percentage of tirzepatide-treated participants experiencing specific TEAE (see [Table GPHN.4.10](#)) by participant TE ADA status (TE ADA+, TE ADA-, TE ADA inconclusive) during the planned treatment period.

Table GPHN.4.10. Adverse Events for Analysis with Immunogenicity Results

TEAE category	Criteria
Hypersensitivity reactions	Anaphylactic reaction SMQ (narrow or algorithm)
	Hypersensitivity SMQ (narrow)
	Angioedema SMQ (narrow)
	Severe Cutaneous Adverse Reaction SMQ (narrow)
	Vasculitis SMQ (narrow)
Injection site reactions	Injection site reaction HLT
	Infusion site reaction HLT
	Administration site reaction HLT

Abbreviations: HLT = High Level Term; MedDRA = Medical Dictionary for Regulatory Activity; SMQ = Standardized MedDRA Query; TEAE = treatment-emergent adverse event.

A listing will be provided for all participants who had ADA Present at any time (including baseline) or had any specific TEAE (see [Table GPHN.4.10](#)). This listing includes a time course of ADA (clinical interpretation result plus flags for samples meeting TE ADA+ criteria and for samples with cross-reactive antibodies and NAb present) along with the TEAE.

Cases of TE ADA that are associated with AEs of either severe/serious hypersensitivity or severe/serious ISR will be classified as AESIs.

Additional immunogenicity analyses as determined later may be presented. The relationship between antibody titers, the PK parameters, and PD response to tirzepatide may also be assessed.

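### Event-driven antibody samples can create or inflate an association in the reaction-by-TE-ADA table, mainly for injection-site reactions

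*Protocol*

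**What the plan says.** **Who is sampled.** Protocol 8.3.2.8 applies to any reported injection-site reaction: "At the time of AE occurrence, samples will be collected for measurement of tirzepatide antidrug antibodies (ADAs) and tirzepatide concentration". It sets no limit on repeats. For systemic hypersensitivity, Protocol 8.9 says that "additional unscheduled samples should be collected as detailed in Section 8.3.2.7". That section is narrower: "In the case of generalized urticaria or anaphylaxis, additional blood and urine samples should be collected as described in Section 10.3". Appendix 3 (10.3) adds a follow-up sample without saying which tests are repeated. Its table of tests includes ADA but is permissive: "Selected test may be obtained in the event of anaphylaxis or systemic allergic/hypersensitivity reactions".

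**Which samples count.** SAP 4.6.5.5.2: "Postbaseline period observations for each participant includes all observations after the first administration of study drug". Nothing restricts this to scheduled visits.

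**What makes a participant positive.** SAP 4.6.5.5.3, first route: "The participant has baseline status of ADA Not Present and at least 1 postbaseline status of ADA Present with titer" at least 2 × MRD, that is 1:20. A detected post-baseline sample without a titer is imputed at 1:20, which meets that limit. Participants with ADA at baseline need a 4-fold rise. A participant is inconclusive if at least 20% of post-baseline samples are inconclusive and the rest show no ADA.

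**What is tabulated.** SAP 4.6.5.5.4: "A summary will be provided of the count and percentage of tirzepatide-treated participants experiencing specific TEAE" by TE ADA status, for hypersensitivity (five SMQs) and injection-site reactions. The sets are mITT, counting tirzepatide exposure time only, and the tirzepatide MTD arm. No test or model is named. The section also plans a participant listing with the ADA time course, and it classes TE ADA with a severe or serious reaction as an AESI.

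**The concern.** Having the outcome adds samples, and each added sample is another opportunity to be classed as exposed. The rule looks for at least one qualifying sample, so more samples can only raise the chance of being TE ADA+. Even if antibodies and reactions were unrelated, reactors could be TE ADA+ more often than non-reactors with the same treatment and follow-up. Neither document restricts status to scheduled samples, accounts for the number of samples, or plans a sensitivity analysis. A reader of the finished percentages could not separate a biological link from a sampling effect, and this table is where the trial would look for such a link.

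**Working it through.** The plan gives no ADA rate, reaction rate or expected association, so there is no figure to reproduce. The check asks what odds ratio the sampling alone would produce if ADA and reactions were unrelated.

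**Inputs from the documents.** The immunogenicity row of the Schedule of Activities has 11 marks: 1 baseline, 8 on treatment to Week 88, the early-discontinuation visit and Visit 801. Four of the eight fall at or before Week 36. In the mITT set, participants later randomized to placebo therefore have about 4 scheduled on-drug samples, against 8 for those continuing tirzepatide. Some column positions after Week 36 look shifted in the text available; the count is intact.

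**Assumptions, not in the documents.** TE ADA+ rate P on scheduled samples (10% to 70%), number of event samples k (1, 2 or 5), correlation between a participant's samples, antibody duration, and a 5% reaction rate.

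**Independent samples.** With m scheduled samples, a reactor with k more has

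P' = 1 − (1 − P)^((m+k)/m), and OR = [P'/(1 − P')] / [P/(1 − P)].

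For P = 50%, m = 8, k = 1: P' = 1 − 0.5^(9/8) = 0.541, so OR = 0.541/0.459 = 1.18. Correlated samples use a beta-binomial model set to the same P at m.

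| P = 50% | k = 1 | k = 2 | k = 5 |
|---|---|---|---|
| m = 8, independent | 1.18 | 1.38 | 2.08 |
| m = 8, correlation 0.3 | 1.08 | 1.15 | 1.36 |
| m = 8, correlation 0.6 | 1.04 | 1.08 | 1.19 |
| m = 8, correlation 0.9 | 1.01 | 1.02 | 1.05 |
| m = 4, independent | 1.38 | 1.83 | 3.76 |
| m = 4, correlation 0.3 | 1.19 | 1.37 | 1.84 |
| m = 4, correlation 0.6 | 1.10 | 1.18 | 1.39 |
| m = 4, correlation 0.9 | 1.02 | 1.05 | 1.09 |

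Across P from 10% to 70%, independent samples with m = 8 give 1.13–1.23, 1.27–1.50 and 1.68–2.60 for k = 1, 2 and 5. Independence is the high end of these models.

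**Antibody duration.** A simulation placed scheduled samples at Weeks 4, 12, 24, 36, 52, 64, 76 and 88. It gave 60% of participants an onset uniform over 88 weeks and placed event samples at random times.

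| Duration | k = 1 | k = 2 | k = 5 |
|---|---|---|---|
| 4 weeks | 1.10 | 1.21 | 1.52 |
| 12 weeks | 1.02 | 1.03 | 1.06 |
| 26 weeks or permanent | 1.00 | 1.00 | 1.00 |

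The last row is expected: the longest gap on that grid is 52 − 36 = 16 weeks, so longer-lasting antibody is found at a scheduled visit anyway.

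**In the table's own terms.** With 5% reactors, P = 50%, m = 8, k = 1 and independence, the reaction percentage is 0.05 × 0.541 / (0.05 × 0.541 + 0.95 × 0.50) = 5.4% in TE ADA+, against 0.05 × 0.459 / (0.05 × 0.459 + 0.95 × 0.50) = 4.6% in TE ADA−. With k = 5 it is 6.6% against 3.3%.

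**Inconclusive rule.** One inconclusive event sample among otherwise clean samples is 1/(4 + 1) = 20% with four scheduled, which reaches the limit. With eight it is 1/(8 + 1) = 11%, which does not.

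**Scheduled samples only.** Then k = 0 for everyone, P' = P, and the sampling-induced odds ratio is 1.00 at equal follow-up under any of these assumptions.

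**The case against.** The strongest reply is that the effect may be too small to matter. Persistent antibody removes it, and one extra sample on eight moves the odds ratio little. Random error is much larger. With an assumed 300 participants, 30% TE ADA+ and 30 reactors, the expected cells are 9, 21, 81 and 189. The standard error of the log odds ratio is √(1/9 + 1/21 + 1/81 + 1/189) = 0.42, a 95% factor of about 2.3 each way; with 15 reactors it is about 3.1. The table is descriptive, and the listing lets a reader see when each positive sample was taken. All of this stands as a limit on size. It does not remove the problem: the bias runs upward or not at all, so it does not average out, and a listing supports case review but does not make the percentages comparable.

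A reader might infer more than the documents support:

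- **That any association in the table will be an artefact.** No antibody rate or persistence is given, and nil is among the possible sizes.
- **That hypersensitivity is affected as much as injection-site reactions.** The operative trigger is generalized urticaria or anaphylaxis and the test wording is permissive, while the table counts five SMQs. Many tabulated events need bring no extra ADA sample.
- **That any positive sample is enough.** The titer limit applies, and baseline-positive participants need a 4-fold rise.
- **That event samples generally push participants into the inconclusive class.** This needs about four or fewer scheduled samples and a drug level at or above assay tolerance, which the documents do not establish.

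**Conclusion.** The point holds as a possible upward bias, mainly for injection-site reactions. Sampling that depends on the outcome, counting of all samples and a one-sample rule are all in the text, with nothing planned against their combined effect. The size cannot be fixed from the documents. It runs from nil with persistent antibody, through about 1.0–1.2 for one extra sample on eight scheduled, to about 2 or more when reactions repeat and samples are close to independent. With only about four scheduled on-drug samples, fewer repeats are needed. These odds ratios rest on assumed rates, correlations and durations, and on every event sample being taken. Movement into the inconclusive class is confined to participants with about four scheduled on-drug samples. This is a low-cost improvement to one descriptive safety table and does not touch the efficacy conclusions.

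**What to change.** In SAP 4.6.5.5.4, add a pre-specified sensitivity version of the TEAE-by-TE-ADA table. Derive status, under both the positive rule and the 20% inconclusive rule, from Schedule of Activities samples only. Flag participants who are TE ADA+ solely on event-driven samples. Keep all samples for overall TE ADA incidence, the listing, AESI classification and case review.

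Show both versions side by side. Scheduled-only status drops the sample closest to the reaction and may miss transient antibody, which is the setting where the bias matters most, so it should not replace the planned table. The cost is a second status flag and one repeat table from data already held, with no change to study conduct.

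Two limits remain. Unequal tirzepatide exposure in the mITT set (about four against eight scheduled on-drug samples) is a separate source of association that this change does not remove. The hypersensitivity sampling triggers in the Schedule of Activities, Protocol 8.3.2.7, 8.9 and Appendix 3 should also be reconciled, so that it is clear which events bring an ADA sample.
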